9.8 Data Handling for MRI data

MRI data will be integrated with MRI data from the MAGNIFY MS trial, which will be handled according to "Data Handling for MRI data – Data handling of Tertiary endpoints" in Section 9 of the MAGNIFY MS IAP version 3.0.

The MRIs will be evaluated by independent central review. The assignment of MRIs to the respective Visits in the parent study was ensured by the central reading process, while this process is not adopted in the Extension Study. Therefore, the statistical analysis will be based on the MRI Visit assignments as provided by central reading for parent study data and MRI Visit assignments as reported in the eCRF for Extension Study data. A 6-months window will be allowed for the Extension Study MRI data. An MRI assessment will be excluded from all analyses if the absolute value of (MRI assessment date – Visit date) > 185 days (which is obtained by 180 [6 months] + 5 [window allowed by protocol]).

All derived lesion counts (except for the Mean T1 Gd+ lesion count) as specified below will be classified as Not Evaluable (NE) if one of the components required for the calculation has been classified as NE by the central reading. The Mean T1 Gd+ lesion count will be set to NE only, if all T1 Gd+ lesion counts that correspond to the respective Period are classified as NE. In all other cases the mean will be calculated based on the available counts during the respective Period.

For definition of Period see Section 9.6 "Study Periods for MRI Assessments".

T1 Gd+ lesion count

- The T1 Gd+ are defined as follow: T1 Gd+ lesion count (by Visit) = T1 Gd+ lesions count from the MRI at the respective Visit.
- Mean T1 Gd+ lesion count (by Period) = sum of all T1 Gd+ lesion counts during the Period /# of scans belonging to the respective Period with non-missing T1 Gd+ lesion count.

All MRI scans belonging to a Period are MRI scans that have been performed during the Period including start and end Visits. For post-Baseline periods starting at Baseline, the Baseline Visit will not be included. For example, Period 48.1 will include all MRI scans during both MAGNIFY MS trial and Extension Study except Screening and Baseline Visit.

- New T1 Gd+ lesion count (by Period)
 - For Periods including up to Month 24 Visit, refer to "Data handling for MRI data: Data handling of Tertiary endpoints" in Section 9 of MAGNIFY MS IAP version 3.0
 - For other Periods ending at Month 36 / Month 48 Visit,
 New T1 Gd+ lesion count = T1 Gd+ lesions count from the MRI at Month 36 / Month 48 Visit due to longer periods

For example: New T1 Gd+ lesion count of the Period between Month 24 and Month 36 (p12.3) is equal to T1 Gd+ lesion count from the MRI at Month 36 Visit.

Active T2 lesion count

As the active (i.e., the new or enlarging) T2 lesion count depends on the length of the Period, it will be presented as reported (non-standardized) and annualized (standardized to 1 years (365.25 days)):

- Period length (days) = MRI date at end of Period MRI date at start of Period +1,
- Annualized active T2 lesion count (by Period) = Total number of active T2 lesions per Period * 365.25/ Period length.

The following types of T2 lesions are defined per Period (standardized and non-standardized):

- Total new T2 lesion count =
 - Total number of new T2 lesions with T1 Gd+
 - + Total number of new T2 lesions without T1 Gd+
- Total enlarging T2 lesion count =

Total number of enlarging T2 lesions with T1 Gd+

- + Total number of enlarging T2 lesions without T1 Gd+
- Total active T2 lesion count =

Total new T2 lesion count

+ Total enlarging T2 lesion count

Note: the number of new or enlarging T2 (with and without T1 Gd+) will be provided by central reading for each of the Periods including the Sequential Visit Periods.

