8.1.1.1 MRI Scanning Procedure

The MRI measures of white matter lesional activity (i.e. new/enlarging T2 lesions or Gd+ T1 lesions) and those of brain atrophy (i.e. the percentage of brain volume change) have shown to be valid surrogate endpoints for clinical outcomes.

Restrictions for the MRI schedule:

In order to prevent interferences caused by a DMD, steroid or adrenocorticotropic hormone (ACTH) administration or by relapse, the following restrictions will apply:

- For any relapse that may require a steroid or ACTH treatment, the MRI acquisition should be planned as scheduled and at least occurring after 30 days of the last dose of steroid/ACTH.
- For any relapse that may require a DMD treatment, if the scheduled MRI is in the next 30 days, acquire MRI in advance before initiation of DMD. If DMD already initiated without possibility to acquire MRI in advance, discuss each case with a Medical Monitor on how to handle the MRI acquisition.

All scans will be performed according to a standard protocol detailed in a separate Image Acquisition Guidelines document. Central imaging core lab will independently perform the analysis of all MRI scans to meet study endpoints. As with other laboratory tests and clinical measures, strict adherence to the MRI scanning protocol, and prompt handling of the scans is essential in obtaining a meaningful result.

Investigator should also ensure that the MRI scan is locally evaluated either by themselves/site radiologist for safety to rule out progressive multifocal leukoencephalopathy and/or any serious central nervous system disease (e.g., tumor, stroke etc.). For participants switching to other DMDs the safety/follow-up will be additionally assessed by the Investigator. Any unscheduled MRI acquired for such switching or for other safety reasons during the study will be analyzed by the Investigator/site radiologist as per standard of care.

Prior to participant assessment, each study site may be asked to send a 'test' or 'dummy-run' scan to assess image quality and shipment procedures, to evaluate the accessibility of the electronic data carrier, and to assess the ability to correctly reposition participants so as to get comparable brain images. Only upon final approval of this test scan, sites will be allowed to begin assessing participants.

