Concomitant procedures which were undertaken any time during the Extension Study Period will be listed by participant for the SAF.

13 Study Intervention: Compliance and Exposure

As no treatment is provided in the Extension Study, participants' compliance and exposure in the MAGNIFY MS trial will be presented for the Extension Study SAF as defined in MAGNIFY MS IAP version 3.0.

14 Efficacy Analyses

The following analyses will be performed based on the FAS except when otherwise stated.

For the detailed definition of covariates and stratification factors that are used in the statistical models see Section 9.10. Details about the derived MRI endpoints and general handling of MRI data is described in Section 9.8.

Descriptive summary statistics will be presented for the absolute values and the changes from Baseline as applicable by Visit [Protocol Scheduled Visits except for Baseline (defined in Section 9.1)] for all efficacy endpoints (and the components, where applicable) for the FAS and respective subgroups for which the variables are analyzed. Details about the presentation of continuous and categorical variables are given in Section 9.

Wherever possible, all estimated results from the statistical models will be calculated with the same observed margin which reflects the population of the whole corresponding analysis set, regardless of missing data (as described in MAGNIFY MS IAP version 3.0).

14.1 Primary Endpoint: Proportion of participants with No Evidence of Disease Activity (three parameter [NEDA-3]) during Year 3 Visit and Year 4 Visit Period after the initial dose of cladribine tablets

The primary endpoint for the Extension Study is defined as the proportion of participants with NEDA-3 during Year 3 Visit and Year 4 Visit Period after the initial dose of cladribine tablets, i.e., NEDA-3 during the following period will be evaluated:

• Year 3 Visit and Year 4 Visit Period (i.e., Extension Study Period)

For the detailed definition of Periods, see Section 9.6.

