14.1.1 Primary Objective: Derivation and analysis of the primary endpoint

No Evidence of Disease activity (NEDA), also referred to as freedom from disease activity, is a new goal that is emerging in MS treatment. NEDA is a composite measure of disease activity, including relapses, cognition and disability progression, and MRI activity.

NEDA-3 during the Extension Study Period is defined as absence of the following three events during the Period:

- Qualifying Relapses
- 6-months Confirmed Disability Progression (6MCDP, see definition below)
- MRI Activity (i.e., presence of T1 Gd+ lesions and/or active T2 lesions)

NEDA-3 will be analyzed with the Kaplan-Meier (KM) time-to-event method to reduce the impact of unknown/missing information.

The start date will be the end date of M24 Visit + 1.

The event date will be defined as the minimum of

- the onset date of the first qualifying relapses during the Extension Study Period
- the start date of the first 6MCDP during the Extension Study Period (see definition below)
- the scan date of the first MRI during the Extension Study Period where at least one T1 Gd+ lesion or at least one active T2 lesion (see Section 9.8 for definition) is identified.

Imputation of partial onset dates of relapses is described in Section 9.7. Since full dates of MRI scan and EDSS assessment are mandatory, partial dates of 6MCDP, or MRI Activity are not expected.

If the participant did not experience any of the three events described above during the Extension Study Period, the minimum of the scan date of the last available MRI, the assessment date of the last available EDSS, and the Extension Study completion/discontinuation date will be used as the censoring date.

The time to disease activity (in months) will be calculated as [event date or censoring date as applicable – start date + 1]/30.4375. The number of participants at risk, failed, and survival rate (i.e., the proportion of participants with NEDA-3) along with the 95% CI will be estimated as per the KM method and reported at 6-months intervals. The KM survival curve will be plotted as well.

A descriptive summary of number and proportion of participants with event (overall and by type of event, i.e., qualifying relapse, 6MCDP, or MRI activity as the earliest event) and censored will be also presented.

6MCDP

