The 6MCDP during Extension Study Period is defined as sustained increase in EDSS score that started during the Period. A Sustained Increase in EDSS score is defined by an increase of:

- at least 1.5 points if the Baseline EDSS score was 0, or
- at least 1 point if Baseline EDSS score was between 0.5 and 4.5 inclusively, or
- at least 0.5 point if the Baseline EDSS score was at least 5,

that occurs over a 6-months' time-period.

The increase will be defined as sustained when it occurs on two post-Baseline Visits during the Extension Study Period that are at least 166 days apart (to be consistent with the parent study minimum visit gap) and no observations at any other visits (including unscheduled visits) in between are less than the defined increase. The assessment date of the earlier of the two EDSS assessments with the defined increase will be defined as the start date of 6MCDP.

For descriptive summaries the following rules will be defined:

Qualifying Relapse

- Yes: any qualifying relapse reported during the Extension Study Period,
- No: Extension study period completed, and no qualifying relapse reported during the Extension Study Period,
- Unknown: otherwise.

6MCDP

• Yes: sustained increase in EDSS score that started during the Extension Study Period,

- No: at least 2 post-Baseline EDSS assessments that are 166 (or more) apart and no sustained EDSS progression that started during the Extension Study Period,
- Unknown: Otherwise.

MRI activity

- Yes: any T1-Gd+ or active T2 observed during the Extension Study Period,
- No: at least one post-Baseline MRI and no T1-Gd+ or active T2 observed during the Extension Study Period,
- Unknown: otherwise.

Analysis (Analysis Set)	Derivation	Statistical Analysis Methods	Missing data handling		
	Primary endpoint: Proportion of participants with NEDA-3 during Year 3 Visit and Year 4 Visit Period after the initial dose of cladribine tablets				

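### The 185-day MRI exclusion in SAP 9.8 also reaches the scan-dated NEDA-3 and time-to-lesion analyses, so lesion activity seen inside the Extension Study Period can go uncounted

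*SAP*

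**What the plan says.** - **The exclusion (SAP 9.8).** "An MRI assessment will be excluded from all analyses if the absolute value of (MRI assessment date" minus Visit date) is above 185 days, a limit "which is obtained by 180 [6 months] + 5 [window allowed by protocol"]. The section also says "The MRIs will be evaluated by independent central review". The central process that assigned scans to visits in the parent study is not used in the extension, which relies on "MRI Visit assignments as reported in the eCRF for Extension Study data".
- **Its reach (SAP 14, introduction).** The efficacy section refers back: "general handling of MRI data is described in Section 9.8".
- **The primary event (SAP 14.1.1).** The MRI component is dated at "the scan date of the first MRI during the Extension Study Period where at least one T1 Gd+ lesion" or active T2 lesion is found. SAP 14.2.1, 14.2.2 and 14.2.3 follow the same pattern. None exempts these analyses from the exclusion, and none of the sensitivity analyses in SAP 14.1.2 restores excluded scans.
- **The crude summary (SAP 14.1.1).** MRI activity is scored No given "at least one post-Baseline MRI and no T1-Gd+ or active T2 observed during the Extension Study Period".
- **Other off-schedule data.** SAP 9.5 keeps out-of-window data and names MRI as the one exception. SAP 9.9 analyses data regardless of protocol deviations.
- **Dates (SAP 9.2).** Only a visit start date (first assessment of the visit) and a visit end date (last assessment) are defined. The Visit date used in 9.8 is neither of these by name.

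**The concern.** A visit window suits tables by visit and annualized lesion counts, where a scan far from its nominal time distorts the figure. A time-to-event analysis that places the event on the scan date does not need that protection. Applied there, the rule removes observations that the endpoint definition would count.

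If the removed scan was active and no other qualifying event exists, the participant becomes either event-free to a later clean scan or censored at an earlier one. In the crude summary, any remaining clean scan is enough to score MRI activity as No. The primary NEDA-3 proportion and the times to first T2 and first Gd+ lesion are all exposed. The trigger is also partly clerical, because it depends on an eCRF label and an undefined date.

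**Working it through.** **1. The plan's own figure.** 180 + 5 = 185 days, as SAP 9.8 states.

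**2. Can a dropped scan lie inside the period?** SAP 9.5 places Visits 1 and 2 at days 360 and 720 after M24. SAP 9.6 runs the Extension Study Period from the day after the M24 visit end date to the M48 visit end date. Taking days 360 and 720 as the visit dates, with |scan day − visit day| > 185:

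| eCRF label | Days dropped within days 1–720 |
|---|---|
| Visit 1 (360 ± 185 = 175 to 545 kept) | 1–174 and 546–720 |
| Visit 2 (720 − 185 = 535 onward kept) | 1–534 |

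All these days are in the period. Day 546 is 720 − 546 = 174 days from Visit 2, so any scan on days 546–720 is dropped if labelled Visit 1 and kept if labelled Visit 2.

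**3. Does the result depend on what Visit date means?** Three illustrations:

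| Scan | Visit start date | Visit end date | Clinic or planned date |
|---|---|---|---|
| Labelled Visit 1, day 560, other assessments day 360 | 560 − 360 = 200, dropped | scan is the end date: 0, kept | 200, dropped |
| Labelled Visit 2, day 500, other assessments day 720 | scan is the start date: 0, kept | 720 − 500 = 220, dropped | 220, dropped |
| Early Withdrawal scan, day 150, mapped to Visit 1 under SAP 9.5 | own withdrawal visit: about 0, kept | about 0, kept | planned day 360: 360 − 150 = 210, dropped |

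So the same scan can be kept or dropped on readings that the SAP leaves open.

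**4. What happens to the event?**
- *Month 36 scan active and dropped, Month 48 clean.* The Gd+ event is lost. SAP 9.6 defines T2 periods from Month 24 to 36, Month 36 to 48, and from parent Baseline, but none from Month 24 to 48. If Month 48 is read against Month 36, the T2 event is lost too and the participant is event-free throughout.
- *Last scan active and dropped.* Censoring moves back to the previous scan. If exclusion is unrelated to what the scan shows, this costs information rather than shifting the estimate. The crude summary still records No if another scan is clean. One participant is worth 100/220 = 0.45 to 100/200 = 0.50 points.
- *Another qualifying event exists.* The failure still counts, possibly on a different date.

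**5. Size of the upward shift.** Inputs are n = 200 to 220 evaluable (Protocol 1.1), yearly activity h = 10% to 30% (assumed) and share f of Month 36 scans excluded = 1% to 10% (assumed). The calculation takes scans at the two nominal visits, all activity detected by MRI, independent years, no other censoring, and Month 48 read against Month 36.

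With all scans used, S = (1 − h)². With exclusion, S* = [1 − h(1 − f)](1 − h). The shift is S* − S = f·h·(1 − h), and the Month 36 events hidden are n·f·h.

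| h | f | Shift in 24-month NEDA-3 | Events hidden (n = 200 to 220) |
|---|---|---|---|
| 10% | 1% | 0.01 × 0.10 × 0.90 = 0.09 points | 0.2 |
| 20% | 2% | 0.02 × 0.20 × 0.80 = 0.32 points | 0.8 to 0.9 |
| 20% | 5% | 0.05 × 0.20 × 0.80 = 0.80 points | 2.0 to 2.2 |
| 30% | 10% | 0.10 × 0.30 × 0.70 = 2.1 points | 6.0 to 6.6 |

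If all the hidden activity were instead found at Month 48 by a read spanning the dropped scan, the 24-month shift would be zero and only the event date would be late. SAP 14.1.1 does not say which period applies.

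For scale, the simple 95% half-width 1.96·√[S(1 − S)/n] is 5.3 points at S = 0.8, n = 220 and 6.9 points at S = 0.5, n = 200.

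**The case against.** The strongest defence is that the window is deliberate and generous. SAP 9.5 names MRI as the exception. Visits have ±30 days and assessments ±5 days, so a 185-day limit should rarely apply. Unscheduled scans for treatment switching or safety are read locally (Protocol 8.1.1.1) and are not the centrally read scans at issue. T2 counts come per period between visit scans, so a visit assignment does matter for them. The study is exploratory. Clean and active scans are dropped alike. All of this stands, and it limits the size. It does not explain why an observed, centrally read, in-period event should be removed from an analysis that uses its actual date.

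Two stronger readings are tempting, and the documents do not support them:

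- *That the protocol makes such timing depend on disease activity.* Protocol 8.1.1.1 asks that after steroids or ACTH the scan stay on schedule, "at least occurring after 30 days of the last dose of steroid/ACTH", and brings a scan forward before a DMD start only when it is due within 30 days. Shifts of about 30 days do not reach 185. Cases where a DMD has already begun are discussed individually with no stated shift, which is no evidence of long ones.
- *That every dropped active scan becomes a NEDA-3 success.* In the day-500 illustration the participant is censored at the earlier scan, not carried to month 24, and on one reading of Visit date the scan is not dropped at all.

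**Conclusion.** The point holds on the text. The exclusion covers the primary and secondary scan-dated analyses, can remove scans that lie inside the period, and depends on an eCRF label and an undefined date. The upward bias needs a specific pattern: Month 36 dropped, Month 48 clean, no other event, and T2 read against Month 36.

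The shift of about 0.1 to 2.1 points rests entirely on the assumed exclusion shares and activity rates, and stays below the confidence-interval half-width even at the top of the range. The documents do not say whether any scan is affected. The change is worth making because it is cheap and protects the primary endpoint, not because a large distortion has been shown.

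**What to change.** 1. In SAP 9.8, limit the 185-day exclusion to by-visit and annualized lesion summaries.
2. In SAP 14.1 and 14.2, for both the Kaplan-Meier analyses and the MRI activity Yes/No rule, use every centrally read scan dated within the period, on its own date. Read active T2 against the last preceding available scan. At a minimum, add this as a sensitivity analysis.
3. State which date Visit date means, including for Early Withdrawal scans mapped to a planned visit.
4. Report the number of scans excluded, by visit label.

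The cost is a few sentences in the SAP and some programming. No new scans are needed, and the existing central reads should serve.

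There is one small downside. SAP 7 treats all Gd+ lesions as new because extension scans are yearly. A scan soon after Month 24 could therefore count a persisting Gd+ lesion as new, so such scans should be flagged.

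### The SAP does not settle whether a scan with a known T2 lesion but a not-evaluable total is a NEDA-3 event, and it lets a not-evaluable scan count as no MRI activity

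*SAP*

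**What the plan says.** **The NE rule.** SAP 9.8 makes every derived lesion count NE "if one of the components required for the calculation has been classified as NE by the central reading". The only exemption is the mean T1 Gd+ count.

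**The active T2 count.** The same section builds the "Total active T2 lesion count" from new and enlarging lesions, each split into those with and without T1 Gd+. That gives four components, and 9.8 notes that "the number of new or enlarging T2 (with and without T1 Gd+) will be provided by central reading". The T1 Gd+ count is a separate quantity: "T1 Gd+ lesion count (by Visit) = T1 Gd+ lesions count from the MRI at the respective Visit".

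**The event.** SAP 14.1.1 dates the MRI event at the first extension scan where "at least one T1 Gd+ lesion or at least one active T2 lesion (see Section 9.8 for definition) is identified". SAP 14.2.1 uses the same wording for the combined parent and extension period. SAP 14.2.2 takes its event date from these two sections. SAP 14.2.3 refers to 9.8 in the same way for time to first new or enlarging T2 lesion.

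**No event.** The primary analysis censors at the earliest of the last available MRI, the last available EDSS and study completion or discontinuation. The SAP does not say whether an NE scan is available in this sense.

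**Descriptive rule.** For the extension period, 14.1.1 gives No for MRI activity with "at least one post-Baseline MRI and no T1-Gd+ or active T2 observed during the Extension Study Period". For the Course 1 and Course 2 periods, 14.2.1 gives No only if at least one T1 Gd+ value and at least one active T2 value exist; otherwise the result is Unknown unless activity was found.

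**The concern.** An NE rule suits a sum, because a sum with an unknown part is unknown. It does not suit an at-least-one question, which one counted lesion already answers. The active T2 variable that 9.8 constructs is the count, with its NE rule attached, and the event definitions point there. A programmer could reasonably flag an event when the derived total is 1 or more. A scan with a known new lesion and one NE component would then give no event.

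The protocol's Schedule of Activities has only two extension MRIs, at Visits 1 and 2. The T2 comparison for the second runs from Month 36 to Month 48 (SAP 9.6), so a lesion that was new by Month 36 is not new again at Month 48. An event missed at the first scan may never be recovered.

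The descriptive rule has a related gap. A scan that is NE throughout has nothing observed on it, so the participant is No. Yet 14.1.2 says that missing results get their own category in the crude summary. The study has one arm, so no comparator offsets an error in one direction.

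**Working it through.** The plan states no figure that depends on this rule, so there is nothing to reproduce. The check is a trace of the rules followed by an illustration of scale.

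**Step 1: the NE rule.** Take a scan with 0 and 3 new lesions (with and without T1 Gd+) and an enlarging count of NE and 0. New = 0 + 3 = 3, enlarging = NE + 0 = NE, total active T2 = NE. With new = NE + 3 and enlarging = 0 + 0, the total is again NE. Three lesions are known in both cases.

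**Step 2: three readings of the event rule for that scan, with no T1 Gd+ lesion recorded.**
- (a) A counted lesion is an identified lesion: event, no bias.
- (b) The derived total decides and the NE scan is available: no event. If this is the last scan, the participant is censored as an event-free completer would be.
- (c) The derived total decides and the NE scan is not available: no event, and censoring falls at an earlier date.

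If the scan has a T1 Gd+ lesion, it is an event under all three.

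**Step 3: descriptive rules side by side.** For a participant whose only scans are NE, the 14.1.1 rule for the extension period gives No. The 14.2.1 Course 1/2 rule requires values and gives Unknown.

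**Step 4: scale.** Assumptions, none from the documents: a share h of those at risk is MRI-positive at each of the two yearly scans; a share q of positive scans has a known T2 lesion, one NE component and no recorded T1 Gd+ lesion; relapse, disability progression and dropout are ignored. With e = h(1 − q), the 2-year Kaplan-Meier estimates are:

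- (a) (1 − h)²
- (b) (1 − e)²
- (c) (1 − e) × [1 − e/(1 − hq)], because participants whose second scan is NE leave the risk set before it

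Example with h = 15%, q = 5%: e = 0.1425. (a) 0.85² = 72.25%. (b) 0.8575² = 73.53%, so +1.28 points. (c) 0.8575 × (1 − 0.1425/0.9925) = 73.44%, so +1.19 points.

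Overstatement against (a), in percentage points, shown as (b) / (c):

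| h | (a) | q = 2% | q = 5% | q = 10% | q = 20% |
|---|---|---|---|---|---|
| 10% | 81.0% | 0.36 / 0.34 | 0.90 / 0.86 | 1.81 / 1.73 | 3.64 / 3.49 |
| 15% | 72.2% | 0.51 / 0.47 | 1.28 / 1.19 | 2.57 / 2.39 | 5.19 / 4.86 |
| 20% | 64.0% | 0.64 / 0.58 | 1.61 / 1.45 | 3.24 / 2.94 | 6.56 / 6.00 |

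In crude percentages, with the 200 to 220 evaluable participants planned in the protocol synopsis, one misclassified participant moves the result by 100/220 = 0.45 to 100/200 = 0.50 points.

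**The case against.** A reader might infer that the SAP makes a scan with known lesions a non-event and counts the participant as activity-free. The documents do not say that.

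- The NE rule governs derived counts, whereas the event turns on a lesion being identified. SAP 9.8 glosses active simply as new or enlarging: "As the active (i.e., the new or enlarging) T2 lesion count depends on the length of the Period". Read literally, a counted new lesion is an event. This stands, and it is why the point is an unsettled rule and not a stated error.
- T1 Gd+ is an independent route to an event. This stands.
- Kaplan-Meier censors a participant without an event; it does not classify that person as free of activity. This stands for the primary estimate. It does not answer the descriptive rule, which does assign No.
- Nothing shows how often central reading returns a mixture of evaluable and NE components, or how a scan without usable contrast is coded. The MRI data transfer specification and the parent-study analysis plan are cited but are not among the documents, and the latter may hold further NE rules. This stands, so no frequency can be claimed.
- The study is exploratory with no formal hypothesis (protocol 9.1). For a proportion near 72% with N = 200, the 95% half-width is about 1.96 × √(0.72 × 0.28/200) = 6.2 points, larger than most entries in the table. This limits the weight of the point. It does not justify leaving a coding choice with a one-way effect open in the primary endpoint.

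**Conclusion.** The point holds as a gap in the event rule plus one rule that is wrong as written.

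- **Gap:** the SAP does not say whether a scan with a known new or enlarging lesion but an NE total is an event. Its reference to 9.8 invites coding from the total.
- **Wrong as written:** the 14.1.1 descriptive rule gives No without requiring an evaluable scan, which is looser than the SAP's own Course 1/2 rule.
- **Also open:** whether an NE scan sets the MRI censoring date.

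The direction is certain. An NE total can remove or delay an event but cannot create one, an unearned No adds to the apparently inactive, and later censoring keeps participants without an event at risk for longer. The size is not known. The 0.3 to 6.6 points across the grid rest entirely on the assumed h and q, and the effect of the event gap is zero under the literal reading. The documents therefore do not support a claim that NEDA-3 will be materially overstated. Correcting the rules before the analysis is worthwhile because it costs little and affects the primary endpoint.

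**What to change.** Add to SAP 9.8 and 14.1.1, for NEDA-3, time to first disease activity and time to first active T2 lesion (T2 components only for the last):

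1. MRI activity is **present** if any evaluable component (T1 Gd+, new T2, enlarging T2) is 1 or more, whatever the status of the others.
2. It is **NE/Unknown** if no component is positive and at least one required component is NE.
3. It is **No** only if T1 Gd+ and active T2 are both evaluable and zero. State whether one such scan is enough at participant level when the other is NE; the Course 1/2 rule asks for one value of each kind.
4. Use the **last evaluable MRI** for the censoring date, and give a date for participants with no evaluable extension scan.
5. Keep the NE rule for lesion-count summaries.
6. For scans without usable contrast, use new and enlarging T2 counts without the Gd split only if the central reader supplies them; otherwise treat the scan as NE. SAP 9.8 shows only split counts, and both halves of the split may be unreadable without contrast, so this needs a check with the imaging vendor.

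Cost: a few sentences, one changed event flag and one changed censoring date. Items 1 to 5 use the counts that 9.8 says central reading provides. NEDA-3 may come out slightly lower, and a few more participants will be Unknown or censored earlier.
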